4.1. Primary Efficacy Objective

The primary efficacy objective of the study is to investigate the efficacy of SI-613 for the treatment of OA knee pain by showing a greater reduction in pain as measured by the WOMAC visual analog scale (VAS) pain subscore over a 12-week evaluation period in subjects treated with SI-613 compared with subjects treated with placebo. The primary efficacy objective will be tested using the null hypothesis that there is no difference in the mean change from the pretreatment measure of pain relief (WOMAC VAS pain subscore) between SI-613 and placebo over 12 weeks.

4.2. Secondary Efficacy Objectives

The secondary efficacy objectives are to investigate the effect of SI-613 on signs and symptoms of OA of the knee versus placebo as assessed by the following:

- WOMAC VAS pain subscore
- WOMAC VAS physical function subscore
- Patient Global Impression of Change (PGIC)
- Proportion of subjects experiencing a >30% or >50% improvement in WOMAC VAS pain subscore
- Outcome Measures in Rheumatology Osteoarthritis Research Society International (OMERACT-OARSI) responder rate
- WOMAC VAS total score
- WOMAC VAS stiffness subscore
- 36-Item Short Form Health Survey (SF-36) physical component score
- Amount of acetaminophen rescue medication consumed for the target knee
- Clinical Global Impression of Change (CGIC)
- Weekly average of daily pain scores
- Physical Activity Scale for the Elderly (PASE)

4.3. Safety Objective

The safety objective of the study is to support the overall safety of SI-613 by examining the following:

- Incidence of treatment-emergent adverse events (AEs)
- Vital signs readings
- Laboratory tests
- Target knee examinations
- Synovial assessment in the target knee by magnetic resonance imaging (MRI)

5. INVESTIGATIONAL PLAN

This is a phase 2, multicenter, randomized, double-blind, placebo-controlled study to evaluate the efficacy and safety of a 3 mL IA knee injection of 30 mg SI-613 given every 4 weeks for the treatment of OA knee pain over 12 weeks. The subject will be followed up for 26 weeks after randomization.

Following screening, approximately 80 subjects will be randomized in a 1:1 ratio to treatment with SI-613 or placebo. Randomization will be balanced based on baseline WOMAC VAS pain subscore, Kellgren-Lawrence (K-L) score, sex, and investigational site. Screening may occur 1 to 2 weeks prior to injection (Week 0). As part of the eligibility assessments, subjects will complete the WOMAC (with the VAS pain subscore being used as part of the eligibility assessment) and report their pain on a 100-mm VAS after a 50-foot walk test at Screening and at Week 0 prior to injection. Subjects will be randomized to receive an injection every 4 weeks, a total of 3 injections of either 1% SI-613 or placebo and followed up for 26 weeks after randomization. Subjects will have clinic visits at Weeks 0, 1, 2, 4, 6, 8, 10, 12, 18 and 26. Subjects will receive injections at Weeks 0, 4, and 8. Because the SI-613 and placebo preparations might be visually distinguished in the syringe caused by the difference of the viscosity, the injections will be administered by an unblinded injecting physician who is experienced in IA injection of the knee. The unblinded injecting physician will be instructed on how to maintain blinding of other study team members and subjects from the treatment, and will be otherwise uninvolved with conducting the study, including outcome assessment. At all visits, a blinded evaluating physician or a back-up blinded evaluating physician will conduct the assessments. Subjects will report their signs and symptoms of knee OA through the WOMAC at all visits and PGIC at all follow-up visits. Subjects will also complete a daily diary recording their pain on the 11-point Numeric Rating Scale (NRS) before bed each evening. In addition, the SF-36 will be completed at Weeks 0, 4, 8, 12, and 26 and the PASE will be completed at all visits. The physician will complete the CGIC at all follow-up visits and an examination of the target knee at all visits. MRI will be taken at screening, Weeks 12 and 26 to monitor synovial changes of the target knee and assessed by an independent central imaging evaluator. Subjects must switch to using acetaminophen as a rescue pain medication if they are currently using other pain medications. Acetaminophen will be provided, and pill counts will be used to assess consumption between visits.

The primary endpoint is the change in target knee pain from baseline (average of scores at Visits 1 and 2) to post-treatment (defined as the repeated-measures model estimated average of post-treatment time points over Weeks 1 through 12), as measured on the WOMAC VAS. Secondary efficacy analyses will include evaluations of the difference between the SI-613 and placebo groups in changes in the WOMAC VAS subscores for physical function, stiffness, and total score; proportion of subjects experiencing a >30% or >50% improvement in pain; OMERACT-OARSI responder rates; PGIC; CGIC; SF-36 physical component score; daily pain score; PASE; and acetaminophen consumption.

The incidence of treatment-emergent AEs and the results of vital signs readings, laboratory tests, target knee examinations, and the synovial assessment of the target knee by MRI will be used to assess safety.

6. SELECTION AND WITHDRAWAL OF SUBJECTS

6.1. Subject Inclusion Criteria

A subject must meet all of the following inclusion criteria to be eligible to enroll in the clinical trial:

- 1. Provides their written informed consent.
- 2. Is willing and able to complete efficacy and safety questionnaires and is able to read and understand study instructions.
- 3. Is a male or female aged 40 to 75 years (inclusive) at the time of informed consent.
- 4. Has a diagnosis at the time of screening of OA of the knee according to American College of Rheumatology (ACR) criteria:
 - Knee pain
 - Plus osteophytes
 - Plus at least 1 of 3 of the following criteria:
 - \circ Age >50 years
 - o Morning stiffness <30 minutes
 - o Crepitus on active motion
- 5. Has had OA pain in the target knee during at least the full 12 months (1 year) immediately preceding the screening visit.
- 6. Has a grade 2 or 3 score on the K-L grading scale based on a bilateral standing anteroposterior (AP) x-ray of the target knee taken no longer than 6 months prior to Screening. Kellegren-Lawrence grading will be assessed based on the following definitions:
 - Grade 2: definite osteophytes and possible narrowing of the joint space
 - Grade 3: moderate multiple osteophytes and definite narrowing of the joint space, some sclerosis and possible deformity of bone ends
- 7. Has a pain score for the target knee of 50 to 90 mm (inclusive) on a 100-mm VAS at Screening and Day 1 before injection 1) for the mean of the 5 questions on the WOMAC VAS pain subscale prior to the 50-foot walk test and 2) on the pain assessment following a 50-foot walk test, which has no time constraint but must be completed without assistance of walking aids or other assistive devices or supports.
- 8. Has a pain score for the contralateral knee of ≤30 mm on a 100-mm VAS at Screening and Day 1 before injection 1) for the mean of the 5 questions on the WOMAC VAS pain subscale prior to the 50-foot walk test and 2) on the pain assessment following a 50-foot walk test, which has no time constraint but must be completed without assistance of walking aids or other assistive devices or supports.
- 9. Is willing to switch to using acetaminophen as a rescue medication if currently using other pain medications.
 - Acetaminophen will be provided for the treatment of breakthrough pain in the target knee. This will be the only pain medication permitted for target knee pain.

• Use of over-the-counter acetaminophen will be permitted for AEs, but the use will be limited to up to 3 days total between each visit for Visits 1 through 4 and up to 5 days total between each visit for Visits 5 through 9.

A maximum of 3000 mg/day total of acetaminophen will be permitted. The use of low-dose aspirin (one to two 81 mg doses/day) for thrombosis prophylaxis is permitted.

- 10. Is willing to suspend the use of combination over-the-counter medications that may contain prohibited medications or acetaminophen.
- 11. Is willing to suspend the use of rescue medication (acetaminophen), for both the target knee and any AEs, from the 2 days before to the end of each study visit.
- 12. Failed at least one pharmacologic treatment (e.g., NSAID) in the management of the target knee OA.

6.2. Subject Exclusion Criteria

The presence of any of the following exclusion criteria excludes a subject from study enrollment:

- 1. Has a body mass index (BMI) greater than or equal to 40 kg/m² at Screening.
- 2. Has any of the following:
 - Grade 1 or grade 4 score on the K-L grading scale for the target knee.
 - Grade 1: doubtful narrowing of the joint space and possible osteophytic lipping
 - o Grade 4: large osteophytes, marked narrowing of joint space, severe sclerosis, and definite deformity of bone ends
 - Grade 3 score on the K-L grading scale for the target knee and exhibits at least 1 characteristic of a grade 4 on the radiograph (large osteophytes, marked narrowing of joint space, severe sclerosis, or definite deformity of bone contour)
 - Current or healing fracture of either leg
 - Medical history of severe bone disease that could affect the lower limbs, either generalized (e.g., osteoporosis) or localized (e.g., osteonecrosis, joint deformity, or meniscal instability affecting either leg)
- 3. Has any of the following in the target knee:
 - Secondary OA resulting from trauma or other diseases
 - History of chondrocyte transplantation
 - History of ligament reconstruction
 - Skin disorder or infection in the injection area of the target knee
- 4. Has had joint replacement of the target knee at any time or a joint replacement of the contralateral knee in 1 year prior to Screening.
- 5. Has diagnosed and treated OA of the hips, spine, or ankle within 2 years or has symptomatic OA of the hips, spine, or ankle at Screening or Week 0 pre-injection.
- 6. Has any of the following, which may affect pain in 1 or both knees:
 - Pain in either lower extremity that is sufficient to interfere with evaluation of the knees

- Inflammatory disease other than OA or septic arthritis of either knee (e.g., joint infection) within 1 year prior to Screening or at Week 0 before injection
- Surgical procedure or invasive procedure (e.g., arthroscopy, joint lavage) in either lower extremity within 1 year prior to Screening
- IA HA injection(s) for the treatment of OA of either knee within 6 months prior to Screening
- 7. Has received an IA injection(s) into any joint other than IA HA (e.g., corticosteroids, chondroitin sulfate, or glucosamine) within 90 days prior to Screening.
- 8. Had IA fluid aspirated from either knee within 7 days prior to the start date of screening.
- 9. Has taken any of the following prohibited medications within 7 days prior to Screening. Unless noted, these medications are prohibited in oral, injectable, and suppository forms, but they can be used in inhaled, nasal, or ophthalmic formulations. Topical administration is permitted except for the lower extremity of the ipsilateral side of the target knee.
 - NSAIDs (DF is prohibited by any route of administration)
 - Medicines for neuropathic pain (e.g., pregabalin, gabepentin)
 - Topical capsaicins
 - Duloxetine (serotonin-norepinephrine reuptake inhibitors)
 - Local anesthesia to either knee (local anesthesia to target knee during SI-613 injection procedure is permitted)
 - Anticonvulsant drugs, herbal medicines with analgesic properties

Subjects who agree to discontinue use of these medications and for whom discontinuation of these medications is medically appropriate may return 7 days after discontinuation to complete screening.

- 10. Has taken any of the following prohibited medications within 28 days prior to Screening. Unless noted, oral, injectable, or suppository administration is prohibited, but topical administration is prohibited only for the lower extremity of the ipsilateral side of the target knee.
 - Opioids (prohibited by any route of administration)
 - Corticosteroids (note that IA administration is excluded within 90 days prior to screening per exclusion criterion #7)
 - Antidepressant medications, antianxiety medications, antipsychotic medications, mood stabilizers, and sleeping drugs

Subjects who agree to discontinue use of these medications, and for whom discontinuation of these medications is medically appropriate, may return 28 days after discontinuation to complete screening.

- 11. Has had any block procedure (e.g., nerve block, epidural block, or facet block) within 28 days prior to the start date of screening.
- 12. Has begun taking an oral chondroprotective agent (chondroitin sulfate or glucosamine) for 14 days prior to Screening. Subjects who have been taking a stable dose on a stable regimen for ≥15 days prior to the start date of screening can continue the stable dose

- during the study. Subjects who agree to stabilize their dose of these medications or to discontinue use of these medications, and for whom the adjustment made is medically appropriate, may return after ≥15 days to complete screening.
- 13. Has begun treatment with any physical therapy (exercise therapy, Tai Chi, massage, balneotherapy, taping, insoles, knee braces, thermal agent, and/or transcutaneous electrical stimulation) for OA of the target knee for 28 days prior to the start date of screening. Subjects who have continued at stable regime for ≥29 days prior to the start date of screening can continue during the study. Subjects who agree to stabilize their therapy regimen or to discontinue therapy, and for whom the adjustment made is medically appropriate, may return after ≥29 days to complete screening. Acupuncture is prohibited for either knee for 7 days prior to the start date of screening.
- 14. Is a female subject who is pregnant or lactating.
- 15. Is a female subject of childbearing potential who is not willing to use adequate contraceptive measures to avoid pregnancy. All sexually active subjects must agree to practice an adequate method of birth control during the study. Adequate methods of birth control include the following:
 - Hormonal contraception
 - Use of at least 1 acceptable barrier method; acceptable barrier methods include diaphragm plus a spermicidal agent or condoms (male or female) plus a spermicidal agent
 - Vasectomy, hysterectomy, bilateral tubal ligation, intrauterine device, and/or an exclusive sexual partner for whom 1 of these methods applies

Female subjects who have not menstruated within the past 2 years are considered postmenopausal and do not need to practice birth control.

- 16. Has a history of aspirin-induced asthma (asthma attacks triggered by NSAIDs, etc.).
- 17. Has a known allergy or contraindication to sodium HA products, any DF preparation, or acetaminophen.
- 18. Has another disease that has been associated with any joint symptoms in the past 2 years (e.g., chondrocalcinosis, gout, psoriasis).
- 19. Has the following exclusionary laboratory test results at Screening:
 - Aspartate aminotransferase (AST) or alanine aminotransferase (ALT) >2.5 times the upper limit of normal (ULN)
 - Creatinine >1.5 times the ULN
 - Positive hepatitis C antibodies or hepatitis B surface antigen
- 20. Has a current malignancy or has received treatment for malignancy within the past 5 years prior to informed consent.
- 21. Has a history of recurrent, severe allergic or immune-mediated reactions or other autoimmune disorders.
- 22. Has any of the following medical conditions that would interfere with safety or efficacy evaluation: uncontrolled diabetes; immunodeficiency syndrome; significant cardiovascular, renal, or liver disease; severe anemia; clotting disorder or other blood diseases; serious infectious disease; fibromyalgia or other systemic chronic pain

disorder; rheumatoid arthritis; anserine bursa; lumbar radiculopathy; neurogenic or vascular claudication; vascular insufficiency of lower limbs; peripheral neuropathy severe enough to interfere with the study evaluations; seizure disorder; dementia; psychosis (or history thereof); current anxiety, depression, or other neuropsychiatric symptoms.

- 23. Has presence or history of alcohol or drug abuse, or tests positive on urine drug screen or for blood alcohol. Subjects should be advised not to drink alcohol within 24 hours of Screening. Positive drug or alcohol tests cannot be repeated.
- 24. Has any other psychiatric, medical, or social condition or situation that, in the opinion of the investigator, is likely to interfere with study conduct, confound interpretation of study results, or adversely affect the balance of benefits and risks of study participation.
- 25. Has a contraindication to receiving an MRI of the target knee or is unwilling to have MRI performed.
- 26. Is currently hospitalized or has a planned hospitalization during the life of the study.
- 27. Is receiving worker's compensation or is currently involved in litigation.
- 28. Has participated in a clinical study of an investigational drug, device, or biologic within 90 days prior to informed consent.
- 29. Any condition that, in the opinion of the investigator, might interfere with the evaluation of the study objectives.

6.3. Subject Withdrawal Criteria

Subjects will be encouraged to adhere to the protocol and complete all required assessments. A subject will be discontinued from the study for any of the following medical or administrative reasons:

- A treatment-emergent AE or considerable worsening of an AE that, in the judgment of the investigator or medical monitor, represents an unacceptable risk to the subject and warrants stopping the subject's participation in the investigational study. The investigator must follow the subject until the AE resolves or satisfactorily stabilizes.
- Pregnancy.
- Death of subject.
- Poor response of a subject to the investigational product such that the investigator determines that the subject needs treatment that excludes them from the protocol.
- A critical deviation from the inclusion or exclusion criteria that leads the investigator or medical monitor to determine that continued injections of SI-613 or placebo are not appropriate for ethical or safety reasons.
- Having joint replacement of the target knee
- Receiving an IA injection into the target knee joint (e.g., HA, corticosteroids, or chondroprotective agents) during the study.
- Participation in another clinical study.
- Development of human immunodeficiency virus infection (as assessed by a positive test for human immunodeficiency virus) or active hepatitis.

- Development or diagnosis of alcohol or other substance abuse.
- If the investigator judges it impossible to continue the study for a subject because
 - o The subject does not comply with protocol requirements
 - o The subject is lost to follow up
 - o There are technical issues at the site
- Investigator discretion at any time.
- Subject's request.
- Sponsor's discontinuation of the study at a site.
- Premature termination of the study by the sponsor.

Any enrolled subjects desiring to discontinue prior to study completion should be encouraged to continue in the study and adhere to the protocol and subsequent regularly scheduled safety and efficacy evaluations. Subjects who are discontinued outside of any scheduled visit will be encouraged to complete the early termination visit at the time of withdrawal. Subjects who are discontinued during a scheduled visit will be encouraged to complete all assessments for both that study visit and the early termination visit at the time of withdrawal. A subject who withdraws following the injection will not be replaced.

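### Section 6.3 requires study exit for four reasons that do not prevent follow-up, so active questioning about new adverse events can stop 7 or 14 days after an injection

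*Combined protocol and SAP*

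**What the plan says.** Protocol Section 6.3 states: "A subject will be discontinued from the study for any of the following medical or administrative reasons". Four entries matter here.

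- Critical eligibility deviation: the trigger is a judgment that "continued injections of SI-613 or placebo are not appropriate for ethical or safety reasons".
- Poor response: the trigger is that "the investigator determines that the subject needs treatment that excludes them from the protocol".
- "Receiving an IA injection into the target knee joint" from outside the study.
- "Having joint replacement of the target knee".

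Two neighbouring entries are narrower. The adverse-event entry applies only where the event "warrants stopping the subject's participation in the investigational study". The non-compliance, lost-to-follow-up and site-problem entry begins "If the investigator judges it impossible to continue the study for a subject because".

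Section 6.3 also asks that subjects who want to leave be encouraged to stay for scheduled evaluations. Subjects discontinued between visits "will be encouraged to complete the early termination visit at the time of withdrawal". Those discontinued at a visit are encouraged to do that visit's assessments and the early termination assessments together. Section 7.2.7 makes the early termination visit a copy of Visit 11.

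Sections 12.5 and 12.5.4.1 record adverse events from consent to the final study visit, or at early termination. Beyond that, the protocol follows the event that caused withdrawal (6.3), adverse drug reactions and serious events (12.5.4.1), clinically significant abnormal results (12.5.4.2) and pregnancies (12.6). Section 12.5.1.2 requires reporting of deaths that come to the investigator's attention during follow-up. Section 12.5.5.1 requires a serious event to be reported within 24 hours of awareness, with no stated end date.

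**The concern.** The consequence in Section 6.3 is wider than the reasons require. The eligibility entry shows it best: its trigger concerns further injections, but its result is removal from the study. The other three describe treatment that a subject can receive while still attending visits. The encouragement to stay is addressed to subjects who want to leave, not to those the protocol removes. No section explicitly defines a status in which injections stop and follow-up continues.

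Safety information is at stake. A subject already injected, possibly against a safety exclusion, would have one encouraged exit visit in place of the remaining knee examinations, laboratory tests and questioning about adverse events. A knee or injection-site reaction that starts after that visit would not be sought. Safety is a stated objective (Section 4.3), and there are about 40 subjects per group (Section 13.1).

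**Working it through.** **Inputs.** Injections are on Days 1, 29 and 57. Visits 3, 4, 5, 6, 7, 8, 9 and 10 are on Days 8 ± 2, 15 ± 2, 29 ± 7, 43 ± 6, 57 ± 7, 71 ± 6, 85 ± 7 and 127 ± 14 (Table 2). The second and third injections are given at Visits 5 and 7 and take those windows.

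**The plan's own figure.** 29 − 1 = 28 and 57 − 29 = 28, which matches the 28-day dosing interval in Section 3.3.3. It serves below only as a yardstick.

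**Formulas.** Days from injection to exit = visit day − day of last injection. Uncovered days = 28 − that number, with a floor of 0. The shortest time pairs the earliest visit with the latest injection, and the longest does the reverse.

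| Exit at | Injection to exit, nominal | With windows | Uncovered of 28, nominal | With windows |
|---|---|---|---|---|
| Visit 3 | 8 − 1 = 7 | 5–9 | 21 | 19–23 |
| Visit 4 | 15 − 1 = 14 | 12–16 | 14 | 12–16 |
| Visit 5, before injection | 29 − 1 = 28 | 21–35 | 0 | 0–7 |
| Visit 6 | 43 − 29 = 14 | 37 − 36 = 1 to 49 − 22 = 27 | 14 | 1–27 |
| Visit 7, before injection | 57 − 29 = 28 | 50 − 36 = 14 to 64 − 22 = 42 | 0 | 0–14 |
| Visit 8 | 71 − 57 = 14 | 65 − 64 = 1 to 77 − 50 = 27 | 14 | 1–27 |
| Visit 9 | 85 − 57 = 28 | 78 − 64 = 14 to 92 − 50 = 42 | 0 | 0–14 |
| Visit 10 | 127 − 57 = 70 | 113 − 64 = 49 to 141 − 50 = 91 | 0 | 0 |

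The 1-day extreme needs, for example, Visit 5 on Day 36 and Visit 6 on Day 37. Exit between visits can come sooner after an injection than the nominal figures. A subject who completes the study is followed nominally 183 − 57 = 126 days after the last injection.

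**Scheduled safety assessments forgone.** Knee examinations occur at every visit to Visit 11, so exit at Visit 3, 4, 6 or 8 gives up 8, 7, 5 or 3. Laboratory sets are at Visits 5, 7, 9 and 11, so it gives up 4, 4, 3 or 2. The early termination visit, if attended, returns one of each.

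**The case against.** The protocol is consistent with itself, and its exit visit is a full one, with laboratory tests, knee examination and MRI. Much is still followed afterwards. A reader might infer that all safety follow-up stops at exit, serious events included. The documents do not support that: known drug reactions and serious events are followed, and Section 12.5.5.1 ties reporting to the investigator's awareness, not to the final visit. A post-exit serious reaction that reaches the investigator is arguably reportable. This narrows the gap to active questioning, mainly about non-serious events.

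A reader might also infer that anyone whose injections stop must leave. That is not supported either. The adverse-event entry applies only when participation itself should end, and Section 13.4.2 counts injections received, visits attended and discontinuations separately. An event that rules out only further injections does not force exit.

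A third tempting reading is that the lost pain scores and MRIs damage the primary result. After knee replacement, target-knee WOMAC and synovial MRI no longer describe the treated joint. After an outside injection or excluded analgesics, both are confounded. Section 13.5.2 already plans multiple imputation by discontinuation reason and classifies certain dropouts as nonresponders.

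Two further objections have some force. The four reasons are not the only ones compatible with visits: HIV infection or active hepatitis, substance abuse and joining another study are similar. Post-exit contact might also be described in consent text that is not visible here. Neither changes what Section 6.3 requires for subjects removed under these four entries.

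**Conclusion.** The concern holds in a limited form and is worth considering. For four reasons that do not prevent follow-up, Section 6.3 requires study exit, and planned collection of new-onset adverse events then ends at a visit that is only encouraged. Nominally, 21 of 28 days are uncovered after exit at Visit 3 and 14 of 28 after exit at Visit 4, 6 or 8. Exit at Visit 10 leaves no shortfall.

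These figures are visit spacing, not measured losses. They assume exit at a scheduled visit, an attended early termination visit, and a 28-day yardstick taken from the dosing interval. The protocol sets no 28-day safety window. The documents give no frequency for these exits, so no total effect on the safety data can be stated. No bias in the primary efficacy estimate is claimed.

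**What to change.** 1. Amend Sections 6.3 and 12.5.4.1. For any subject who leaves within 28 days of an injection and has not withdrawn consent to contact, add one adverse-event telephone contact at least 28 days after the last injection. The earliest nominal days are 1 + 28 = 29, 29 + 28 = 57 and 57 + 28 = 85. This also covers early leavers under the other entries.

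2. In Section 6.3, for a critical eligibility deviation, poor response or an outside injection into the target knee, stop study injections. Invite the subject to the remaining scheduled visits for adverse events, knee examination and laboratory tests, and allow any treatment that is needed. After target-knee replacement, collect adverse events and laboratory tests only.

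3. Make WOMAC and MRI after prohibited treatment optional and flag them. State before unblinding whether such WOMAC data enter the primary model. Keep the imputation planned in Section 13.5.2.

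The cost is a short amendment with matching consent wording, some visits already in the schedule, and a few telephone calls. Some subjects will decline. If the sponsor wants only one change, the telephone contact is the cheapest and can stand alone.
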